### 8.3.9 REPORTING OF PREGNANCY

Pregnancy is not considered an adverse event, but subjects that become pregnant prior to completion of study ILIT treatment will be discontinued from treatment. Those patients may continue follow-up procedures through the end-of-study. Pregnancy is required to be reported to the IRB as an UP, in accordance with the procedures in section 8.4.

## 8.4 UNANTICIPATED PROBLEMS

### 8.4.1 DEFINITION OF UNANTICIPATED PROBLEMS (UP)

The Office for Human Research Protections (OHRP) considers unanticipated problems involving risks to participants or others to include, in general, any incident, experience, or outcome that meets **all** of the following criteria:

- Unexpected in terms of nature, severity, or frequency given:
  - a) the research procedures that are described in the protocol-related documents, such as the Institutional Review Board (IRB)-approved research protocol and informed consent document; and
  - b) the characteristics of the participant population being studied;
- Related or possibly related to participation in the research (“possibly related” means there is a reasonable possibility that the incident, experience, or outcome may have been caused by the procedures involved in the research); and
- Suggests that the research places participants or others at a greater risk of harm (including physical, psychological, economic, or social harm) than was previously known or recognized.

### 8.4.2 UNANTICIPATED PROBLEM REPORTING

The investigator will report unanticipated problems to the reviewing IRB using the IRB’s UP report portal and will include the following information:

- Protocol identifying information: protocol title and number, PI’s name, and the IRB project number;
- A detailed description of the event, incident, experience, or outcome;

- An explanation of the basis for determining that the event, incident, experience, or outcome represents an UP;
- A description of any changes to the protocol or other corrective actions that have been taken or are proposed in response to the UP.

To satisfy the requirement for prompt reporting, UPs will be reported using the following timeline:

**To be reported Immediately:**

- Changes in research that were initiated without IRB review and approval to eliminate apparent immediate hazards to the human subjects to ensure the continued safety and welfare of subjects
- Any significant new findings developed during the course of the research and after study completion which may relate to the subject's willingness to continue participation will be provided to the subjects.
- Modifications to previously approved documents
- Receipt of Investigator/Site 483, Determination letter or Warning letter
- If the Principal Investigator's medical license is suspended, revoked, placed on probation or restricted in any state or country
- Safety information that may help to provide additional protections for subject's safety and well-being, throughout the course of the study and after study completion.
- Communication of results from a research study to subjects when those results directly affect their safety or medical care
- Reports of pregnancy

**To be reported within 10 (calendar) days of discovery:**

- Unanticipated problems reports – Unanticipated problems should be reported regardless of whether they occur during the study, after the study completion, or after participant withdrawal or completion. Unanticipated problems involving risks to human subjects or others that are (1) unexpected (in terms of nature, severity, or frequency) given (a) the research procedures that are described in the protocol-related documents, such as the IRB-approved research protocol and informed consent document; and (b) the characteristics of the subject population being studied; (2) related or possibly related to participation in the research (possibly related means there is a reasonable possibility that the incident, experience, or outcome may have been caused by the procedures in the research); and (3) suggests that the research places subjects or others at a greater risk of harm (including physical, psychological, economic, or social harm) than was previously known or recognized. Examples of problems or events that may meet the definition of unanticipated problems involving risk to subjects or others may include, but are not limited to the following:
  - Imminent threat of a reportable event that has not yet occurred
  - Information indicating a change to the risk/benefit ratio of the research
  - Death
  - Breach of confidentiality, including lost or stolen study documents/data
- Non-compliance issues – such as failure by the sponsor-investigator or a sub- to follow the IRB's requirements, applicable regulations or to protect human research subjects, including but not limited to the principles of the Belmont Report
- Serious non-compliance issues – non-compliance as defined as above and as determined to be serious in a way that adversely affects the rights and welfare of human subjects following the investigation and review by the IRB

- Continuing non-compliance issues – a pattern of repeated non-compliance or serious non-compliance as determined by the IRB
- Significant deviations – those that deviate from the approved protocol, informed consent process and affect or can potentially affect the safety of subjects.
- Revisions to the report of prior investigations, as applicable

### 8.4.3 REPORTING UNANTICIPATED PROBLEMS TO PARTICIPANTS

Reporting of UP to study participants will occur as required in accordance with the IRB's procedures and at the IRB's direction in accordance with the IRB's written procedures.

## 9 STATISTICAL CONSIDERATIONS

Statistical analysis will be performed by the sponsor-investigator or qualified designee using appropriate statistical analysis software. Analyses requiring significance testing will be two-sided at a 5% significance level, unless otherwise specified. All confidence intervals will be two-sided 95% confidence intervals.

Before unblinding, the programming and testing of the analysis programs and datasets will be completed in accordance with the specifications within the protocol. Assessment tools, including the TSS, TCS, DMS, DSS, NRS-11, and other PROs are attached in Appendix 3.

### 9.1 STATISTICAL HYPOTHESES

The null hypothesis for the primary and secondary endpoints is the equality of ILIT treatment with allergenic extract and intranodal injection of placebo (diluent) control. The null hypothesis for the safety endpoints is that ILIT treatment with allergenic extract is non-inferior to placebo. To control for multiplicity, efficacy tests will be performed stepwise in pre-specified order of hypotheses to be tested. Post-hoc and exploratory analyses will be noted as such in the publication of trial results.

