**3 OBJECTIVES AND ENDPOINTS**

OBJECTIVES	ENDPOINT(S)	JUSTIFICATION FOR ENDPOINT
Primary		

To evaluate the safety of ILIT for Mountain Cedar pollinosis relative to placebo control based on the proportion of subjects receiving allergenic extract versus the proportion of subjects receiving placebo that:
 
 
1. experience anaphylaxis, or
 
2. are treated with epinephrine, or
 
3. experience any other treatment-emergent, serious adverse event (SAE) within 60 minutes of the ILIT procedure.
 
	
 
1. Relative proportion of subjects experiencing a serious, treatment-emergent AE up to 60 minutes after the ILIT procedure.
 
	
Risk of anaphylactic reactions is inherent in AIT and dose adjustments are required to continue therapy. This study will evaluate the frequency of these and related serious, treatment-emergent reactions to understand whether the individualized starting dose yields a safety profile for ILIT treatment of mountain cedar allergy that is consistent with other immunotherapies. Rates of anaphylactic reactions following in studies of SCIT and SLIT have been reported at about 1% of patients, which is similar to the frequency across all previous studies of ILIT.

Secondary		

 
1. To evaluate the efficacy of ILIT relative to placebo during the 2018-2019 Texas Mountain Cedar allergy season using total combined score (TCS), a composite of the daily symptoms score (DSS) and daily medication score (DMS).
 
	
 
1. Difference in reported average daily total combined score (TCS) between ILIT and placebo groups during the 2018-2019 Mountain Cedar pollen season. Relative number of days during the allergy season that TCS is lower in the ILIT group relative to the placebo group.
 
	
The European Academy of Allergy and Clinical Immunology (EAACI; Pfaar et al., 2014) recommends the TCS, a composite of daily symptom score (DSS) and daily medication score (DMS) as the standard primary endpoint for randomized controlled trials in AIT for allergic rhinoconjunctivitis. This endpoint has been used in previous pivotal trials of AIT (for an example see Blaiss et al. 2010).

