#### 9.4.4 SAFETY ANALYSES

Safety analyses will compare treatment groups using appropriate methods according to their nominal or quantitative nature. The total safety score (TSS) and proportion of subjects with any treatment-emergent SAE, as defined in the composite safety endpoint, will be assessed using the Mann-Whitney test. Data will be presented in the form of descriptive statistics and appropriate tables and graphs with a conclusion on whether the significance level allowed the null hypothesis for each test to be rejected.

---

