1. INTRODUCTION

This Statistical Analysis Plan (SAP) describes the planned analysis and reporting for the TX-SMILE study, number TASC-ILIT-MC-2018, an investigator-initiated, multi-center, randomized, double-blind, parallel-group, placebo-controlled study to evaluate the safety, tolerability, and efficacy of an alternative injection site and associated adjustments to dosing and treatment regimen for allergen immunotherapy with a commercially-available, FDA-approved allergenic extract for the immunotherapy treatment of allergic rhinitis and conjunctivitis due to pollen from the conifer Mountain Cedar.

This investigation is a phase 2 proof-of-concept study to evaluate an alternative injection site location (inguinal lymph node versus subcutaneous injection into the upper aspect of the arm) with an associated reduction in the extract dose and number of injections required for treatment of seasonal allergic rhinitis and conjunctivitis due to the conifer Mountain Cedar using an FDA-approved, commercially available product, Mountain Cedar pollen allergenic extract (ALK-Abelló, Inc., Port Washington, NY 11050; US Government License No. 1256).

The structure and content of this SAP is intended to provide sufficient detail to meet the requirements identified by the Food and Drug Administration (FDA) and International Conference on Harmonization of Technical Requirements for Registration of Pharmaceuticals for Human Use (ICH): E9 Guidance on Statistical Principles in Clinical Trials. All work planned and reported for this SAP will follow accepted guidelines and standards, as published by the American Statistical Association.

The following documents were reviewed as the basis for preparation of this SAP;

- Clinical Study Protocol TASC-ILIT-MC-2018
- Case Report Form (CRF) for TASC-ILIT-MC-2018
- ICH E9 Guidance on Statistical Principles for Clinical Trials
- ICH E6 Structure and Content of Clinical Study Reports
- ICMJE Recommendations for Manuscript Preparation
- CONSORT Statement and Checklist for Reporting Clinical Trial Results

The reader of this SAP is encouraged to read the clinical study protocol for additional details on the conduct and operations of the study. Discrepancies between definitions

Statistical Analysis Plan

or explanations between the SAP and protocol will be described. For analytic purposes, definitions in the SAP will prevail.

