6.7 Multiplicity

There is a single primary endpoint, with a single primary hypothesis test, so no adjustment for multiplicity is needed for the primary endpoint.

To adjust for multiplicity among the secondary endpoints, a fixed testing order will be used. The secondary endpoints will be tested in the pre-specified order, if the primary endpoint is found to be statistically significant. Testing will proceed to the next endpoint if the preceding endpoint is found to be statistically significant at the 5% (two-sided) level. The moment an endpoint is found not to be significant at the 5% (two-sided) level, all remaining endpoints will be considered exploratory, instead of confirmatory. No adjustment for multiplicity will be made for the exploratory endpoints.

The Holm-Bonferroni correction will be used for pre-specified multiple comparisons due to correlation between endpoints based on the TCS.

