10. SAFETY ANALYSIS

Safety analyses will compare treatment groups using appropriate methods according to their nominal or quantitative nature and will include descriptive statistics rather than formal hypothesis testing for noninferiority due to the small overall sample size. The study included a formal stopping rule in the event two systemic allergic reactions were detected.

The total safety score (TSS) and proportion of subjects with any treatment-emergent SAE, as defined in the composite safety endpoint, will be assessed using the Mann-Whitney test. Data will be presented in the form of descriptive statistics and appropriate tables and graphs with a conclusion on whether the significance level allowed the null hypothesis for each test to be rejected.

Safety Objective: To evaluate the safety profile of ILIT versus placebo using a standardized scoring system, the Total Safety Score worksheet, for AEs of interest (AEIs) up to 60 minutes post-procedure.

Statistical Analysis Plan

Safety Endpoints:

- Proportion of subjects experiencing a serious, treatment-emergent AE up to 60 minutes after an intranodal injection procedure
- Proportion of subjects experiencing systemic reactions to ILIT relative to placebo and severity of reactions relative to placebo as assessed by the Total Safety Score (TSS)
- Proportion of subjects reporting local injection site reactions relative to placebo and severity of local reactions relative to placebo, as assessed by the TSS

Additional safety tables and listings will include summaries of all patients experiencing anaphylaxis or treated with epinephrine, by group and a table of TSS reactions by severity by group.

Safety Population:

Safety analysis will include all participants who received at least one dose of study intervention regardless of whether they provided any diary data.

Calculation cumulative safety score (sum of TSS) across all patients by group will be performed in accordance with the scoring instruction described in section 7.4

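### The only stated safety null is reversed (non-inferiority, with no margin), and SAP 10 still asks for a reject/not-reject verdict on serious events that says almost nothing at true rates up to about 10%

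*Protocol*

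**What the plan says.** Protocol Section 3 makes safety the primary objective, with this endpoint: "Relative proportion of subjects experiencing a serious, treatment-emergent AE up to 60 minutes after the ILIT procedure". The objective covers anaphylaxis, epinephrine treatment and any other serious treatment-emergent event in that window. Protocol 9.4.2 ranks efficacy behind safety.

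On hypotheses, Protocol 9.1 states: "The null hypothesis for the safety endpoints is that ILIT treatment with allergenic extract is non-inferior to placebo". Neither document gives a margin.

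On the test, Protocol 9.4.4 says that the Total Safety Score (TSS) and the "proportion of subjects with any treatment-emergent SAE, as defined in the composite safety endpoint, will be assessed using the Mann-Whitney test". Protocol 9 sets tests at 5%, two-sided, unless otherwise specified.

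SAP 10 says first that the safety analyses "will include descriptive statistics rather than formal hypothesis testing for noninferiority due to the small overall sample size". Its next paragraph repeats the Protocol 9.4.4 text: Mann-Whitney for the TSS and for the serious-event proportion, and "a conclusion on whether the significance level allowed the null hypothesis for each test to be rejected". It does not say what that null is. SAP 1 gives the SAP priority: "For analytic purposes, definitions in the SAP will prevail".

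**The concern.** A non-inferiority claim is earned by rejecting the hypothesis that the treatment is worse by at least a stated margin. Protocol 9.1 puts the favourable statement in the null instead. Too few patients, or too few events, then help to keep it, because failing to reject leaves non-inferiority standing. The two-sided Mann-Whitney test does not match that null either, since it addresses equality.

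SAP 10 repairs half of this. It withdraws formal non-inferiority testing, then asks for a verdict on a null that it never states. SAP priority cannot settle the matter, because the conflict lies inside SAP 10 and the only safety null on paper is the one in Protocol 9.1. At stake is the reported conclusion on the primary-objective endpoint: a non-significant result could be written up as non-inferiority retained.

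**Working it through.** **Inputs.** Two-sided alpha 0.05 (Protocol 9). Up to 16 per group, 23 required (Protocol 9.2, SAP 5.1); 12 v 11 is my split of 23. About 1% anaphylaxis with other immunotherapy (Protocol Section 3). No event rate is assumed for either arm in the documents. I take the placebo rate as 0 unless stated.

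**The plan's own figure.** There is no power, margin or sample size for safety. The stated 23 is for efficacy, and it reproduces: with f² = 0.50 and two predictors, a noncentral F test with 2 and N − 3 degrees of freedom and noncentrality 0.50 × N has power 0.788 at N = 22 and 0.810 at N = 23. It says nothing about serious events.

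**Events needed to reject, 16 v 16, none on placebo.** With x ILIT events, U = 16x + 16(16 − x)/2 and its null mean is 128.
- Mann-Whitney (tie and continuity corrected), x = 3: U = 152, SD = 13.40, z = (24 − 0.5)/13.40 = 1.75, p = 0.080.
- Mann-Whitney, x = 4: U = 160, SD = 15.21, z = (32 − 0.5)/15.21 = 2.07, p = 0.038.
- Fisher, x = 4: 2 × C(16,4)/C(32,4) = 2 × 1820/35960 = 0.101.
- Fisher, x = 5: 2 × C(16,5)/C(32,5) = 2 × 4368/201376 = 0.043.

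So Mann-Whitney needs 4 events and Fisher 5. At 12 v 11 the thresholds are the same: Mann-Whitney p = 0.044 at 4 events, Fisher p = 0.093 at 4 and 0.037 at 5.

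**Chance of rejecting.** This is P(X ≥ 4) for Mann-Whitney and P(X ≥ 5) for Fisher, with X binomial on the ILIT arm:

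| True ILIT rate | 16 v 16, Mann-Whitney | 16 v 16, Fisher | 12 v 11, Mann-Whitney | 12 v 11, Fisher |
|---|---|---|---|---|
| 5% | 0.7% | 0.1% | 0.2% | 0.02% |
| 10% | 6.8% | 1.7% | 2.6% | 0.4% |
| 20% | 40% | 20% | 21% | 7% |
| 23% | 52% | 30% | 29% | 12% |
| 27% | 66% | 44% | 41% | 20% |

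With 1% on placebo at 16 per arm, the 10% row becomes 5.9% and 1.5%, and the 20% row 35% and 18%. An 80% chance of rejecting (placebo rate 0, 16 per arm) needs a true ILIT rate of 31.8% (Mann-Whitney) or 38.5% (Fisher).

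The 23% and 27% rows come from the dust-mite and pet-allergen ILIT study in Protocol 2.2. Three subjects had moderate-to-severe systemic reactions, 13 were enrolled and 11 completed: 3/13 = 23%, 3/11 = 27%. Counting all three towards the composite is an assumption.

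**If the rate is low.** Taking 1% as the composite rate (an assumption, since the quoted figure is anaphylaxis only), the chance of no event in either arm at 16 per arm is 0.99^32 = 72% with 1% in both arms, or 0.99^16 = 85% with 1% on ILIT and none on placebo. There is then nothing to test.

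**What zero events would show.** The exact two-sided 95% upper limit for 0/n is 1 − 0.025^(1/n): 20.6% at n = 16 and 26.5% at n = 12. For 0/16 v 0/16 the Newcombe upper limit of the difference is 19.4 points. Even the best possible result would not exclude an excess of 10 or 15 points (illustrative margins, as none is stated).

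**The case against.** The strongest reply is that the SAP has already dealt with this. It prevails for analysis, it recognises that the sample is too small, and it withdraws formal non-inferiority testing. What remains looks like one paragraph carried over from Protocol 9.4.4. That is fair as far as it goes: the non-inferiority test is superseded. But the carried-over paragraph is current text, and it still demands a verdict against a null.

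Second, the trial is exploratory (Protocol 9.4.1, SAP 6.6), and nothing says that non-rejection will be reported as proof of safety. This stands and lowers the weight of the point. A reader might infer that the trial plans to claim non-inferiority; the documents do not say so. They only leave that reading open.

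Third, the 1% rate is the most favourable comparison for this criticism. The dust-mite and pet-allergen study suggests that higher rates are possible, and at 23% to 27% the Mann-Whitney test at 16 per arm would reject 52% to 66% of the time. This stands too, so the claim of near-uninformativeness must stop at low rates.

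Two further criticisms are tempting but fail. One is that the applicable null is ambiguous because Protocol 9.1 also says "The null hypothesis for the primary and secondary endpoints is the equality of ILIT treatment with allergenic extract". Safety endpoints have their own sentence there, and the list that follows puts the serious-event proportion first among them. The other is that safety is missing from the testing order. Protocol 9.1 confines the stepwise procedure to efficacy tests, and SAP 6.7 follows it: "There is a single primary endpoint, with a single primary hypothesis test". That is by design.

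**Conclusion.** The point holds in limited form. The safety null in Protocol 9.1 is reversed and has no margin. SAP 10 drops the non-inferiority test but keeps a reject/not-reject conclusion on serious events, with no other safety null to attach it to. For true ILIT rates up to about 10%, the chance of rejecting is 7% or less at 16 per arm and 3% or less at 12 v 11, so non-rejection is nearly uninformative. At higher rates the test has some power, but non-rejection still does not show non-inferiority at any rate. These figures rest on a placebo rate of 0 or 1% and on the stated maximum of 16 per group or my 12 v 11 split.

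The finding should not be extended to the TSS. That score also counts local reactions, which may be common, and the documents give no assumed placebo rate from which to judge the power of its test. Nor does it mean that patients are less protected: Protocol 8.2 has a separate hold rule that does not use this test. The primary efficacy analysis is unaffected. This is a correction that should be made to how the primary-objective endpoint is reported.

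**What to change.** - SAP 10: delete the Mann-Whitney test and the reject/not-reject conclusion for the serious-event proportion. Make the same deletion in Protocol 9.4.4, or record the discrepancy in a SAP note, as SAP 1 provides.
- Protocol 9.1: delete the non-inferiority safety null, or disown it expressly in the same SAP note.
- Report serious events per arm with exact two-sided 95% confidence intervals and an exact interval for the difference.
- If the TSS test is kept, state a two-sided null of equality, label the test exploratory, and say that non-rejection is not evidence of safety or non-inferiority.

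The cost is wording only; no data, visits or sample size change. Counts by group are largely planned already, and two-sided 95% intervals are already the standard in Protocol 9. The trial gives up a significance statement on serious events that its size cannot support.

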#### Safety Endpoints:

1. Proportion of subjects experiencing a serious, treatment-emergent AE up to 60 minutes after the ILIT procedure.
2. Proportion of subjects experiencing systemic reactions to ILIT relative to placebo and severity of reactions relative to placebo as assessed by the Total Safety Score (TSS)
3. Proportion of subjects reporting local injection site reactions relative to placebo and severity of local reactions relative to placebo, as assessed by the TSS

